## **7.2.2 Primary endpoint analyses**

The primary analysis of the primary endpoint will be performed using multiple comparison and modelling techniques (MCPMod), whereby several possible dose response models (patterns) will be evaluated while keeping full control of the type I error at 5% (one-sided), to identify the best-fitting model or subset of models.

[figure not shown]
A logistic regression analysis will first be carried out on the primary endpoint. Covariate-adjusted estimates of the log odds for each dose and the covariance matrix will be extracted from the logistic regression fit and used for the subsequent MCPMod analysis. The MCPMod analysis will be carried out on the logit scale, and the results converted back to the original response scale for interpretation. The logistic regression model will be fitted without an intercept and will include presence of diabetes of any type (yes, no) and baseline fibrosis stage (F1, F2, F3), as well as the dose group, as factors.

The basic shape of each of the models to be tested must be pre-defined. The following model assumptions and resulting graphs ([Figure 7.2.2: 1](#)) have been selected to cover a plausible and

diverse range of dose response patterns, with placebo response rate assumed to be 20% [[R16-5487](#); [R16-5489](#); [R18-2781](#)] and maximum BI 456906 response rate assumed to be 45%. The maximum BI 456906 response rate occurs at the highest BI 456906 dose under monotone assumptions; one non-monotone dose response pattern is also included here, to allow for the possibility that this is not the case. Note: specifications here are made on the original response scale, but the MCPMod analysis itself must use the logit scale, i.e., in which the assumed placebo response rate is  $\log(0.20/(1-0.20))$  and the maximum BI 456906 response rate is  $\log(0.45/(1-0.45))$ :

- Linear
- Exponential1: 25% of maximum effect achieved at dose 3.0 mg (Note: a 3.0 mg dose is only used to specify the models here and below. This dose is not proposed for inclusion in the trial.)
- Exponential2: 5% of maximum effect achieved at dose 3.0 mg
- Emax1: 50% of maximum effect achieved at dose 3.0 mg
- Emax2: 80% of maximum effect achieved at dose 3.0 mg
- Quadratic: Maximum effect achieved at dose 4.8 mg.

Figure 7.2.2: 1 Dose response patterns considered for the MCPMod analysis of the primary endpoint

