### 7.2.3 Secondary endpoint analyses

#### MRI-PDFF responder secondary endpoint

MCPMod analysis of the secondary endpoint of 30% reduction in liver fat content assessed by MRI-PDFF at Week 48 will be performed in the same way as for the primary analysis in [Section 7.2.2](#), and where the methodology is the same, it is not repeated here.

Covariate-adjusted estimates of the log odds for each dose and the covariance matrix will be extracted from a logistic regression fit and used for the MCPMod analysis, similarly to the primary analysis in [Section 7.2.2](#). The same baseline factors will be used in the logistic regression model, plus an additional linear covariate for baseline liver fat content (from MRI-PDFF).

The same model assumptions and resulting graphs will be used as specified in [Section 7.2.2](#) for the primary endpoint, except that the placebo response rate is assumed to be 15% and the maximum BI 456906 response rate is assumed to be 50%. As before, the MCPMod analysis itself must use the logit scale, i.e., in which the assumed placebo response rate is  $\log(0.15/(1-0.15))$  and the maximum BI 456906 response rate is  $\log(0.50/(1-0.50))$ .

The analysis of this secondary MRI-PDFF responder endpoint will be performed using the FAS, and will use the actual maintenance dose (i.e., as treated).

[REDACTED]

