#### Other secondary endpoints

For the continuous secondary endpoints measured repeatedly over time, a mixed model for repeated measures (MMRM) analysis will be performed and used to obtain covariate-adjusted mean estimates of differences between active BI 456906 doses and placebo at Week 48. The MMRM will include fixed effects for the baseline value of the endpoint (i.e., baseline liver fat content or baseline NAS, as relevant) and baseline by visit interaction as continuous covariates, and treatment, presence of diabetes (yes, no), baseline fibrosis stage (F1, F2, F3), visit and treatment-by-visit interaction as factors. Unstructured covariance will be used to model the relationship between pairs of endpoint measurements taken at different visits on the same patient. The Kenward-Roger approximation will be used to estimate the

denominator degrees of freedom. The TSAP will specify approaches to be taken to resolve possible non-convergence issues, including, if necessary, the selection of a simpler covariance structure.

For the binary secondary endpoint of a one stage decrease in fibrosis stage after 48 weeks, a logistic regression analysis will be performed and used to obtain covariate-adjusted odds ratios between active BI 456906 doses and placebo. The logistic regression model will include the same model terms as specified in [Section 7.2.2](#). Where biopsy data are available between Week 40 and Week 48 for patients who prematurely discontinued early, these data will be used directly to determine the response for such patients (similarly to Section 7.2.2).

MCPMod dose finding analyses are not planned to be performed for secondary endpoints, other than as specified above for the MRI-PDFR responder endpoint. If additional MCPMod analyses are required, these will be specified in the TSAP, together with the dose response shapes to be evaluated.

All secondary endpoints will be summarised descriptively.

Secondary endpoints will be analysed using the FAS.

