5. ENDPOINTS

5.1 PRIMARY ENDPOINT(S)

The primary endpoint is the improvement (yes/no) from baseline in histological findings based on liver biopsy after 48 weeks of treatment. In practice, patients who discontinued treatment early but after 40 weeks of treatment are expected to have a post-baseline liver biopsy performed, and will also contribute to the primary endpoint derivation.

Patients are expected to have $NAS \geq 4$ and a fibrosis stage of F1a, F1b, F1c, F2 or F3 at baseline, according to the entry criteria for the trial.

Improvement in histological findings is defined as a composite of:

1. Improvement in NASH:
 - Decrease of at least 2 points in NAS, with at least 1 point decrease in NAS sub-score of either lobular inflammation or ballooning,

and

2. No worsening of fibrosis
 - Absence of any increase in fibrosis stage.

The NAS and fibrosis scoring system is summarized below. Details of the meaning of each grade/stage are referred to the CTP.

Table 5.1: 1 NAS scoring system for liver biopsies

| | Steatosis | Lobular Inflammation | Ballooning | NAS (Total Score) |
|--------------|------------------|-----------------------------|-------------------|--------------------------|
| | Grade 0 | Grade 0 | Grade 0 | |
| | Grade 1 | Grade 1 | Grade 1 | |
| | Grade 2 | Grade 2 | Grade 2 | |
| | Grade 3 | Grade 3 | | |
| Range | 0-3 | 0-3 | 0-2 | 0-8 |

The total score for NAS is the sum of the 3 NAS sub-scores for steatosis, lobular inflammation and ballooning respectively.

Table 5.1: 2 Fibrosis staging for liver biopsies

| | Fibrosis stage | Fibrosis score |
|--------------|-----------------------|-----------------------|
| | Stage F0 | 0 |
| | Stage F1a | 1 |
| | Stage F1b | 1 |
| | Stage F1c | 1 |
| | Stage F2 | 2 |
| | Stage F3 | 3 |
| | Stage F4 | 4 |
| Range | | 0-4 |

The fibrosis score is the same as the assigned stage of fibrosis without the distinction whether a stage of F1a, F1b or F1c was recorded (for a fibrosis score of 1). A patient who has a baseline fibrosis stage of F1a, F1b or F1c and a different post-baseline fibrosis stage of F1a, F1b or F1c is not considered to have worsening or improvement in fibrosis.

Central pathology readings of biopsy slides will be used. These will be physical central pathology readings for patients at sites in all countries, except in China where digital central pathology readings will be used for baseline in the primary endpoint definition (see further below).

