7.1 DEMOGRAPHIC AND OTHER BASELINE CHARACTERISTICS

Descriptive summaries of the following demographic variables and characteristics measured at baseline will be presented, to include: sex, race and ethnicity, age (years) (continuous and categories), height (cm), weight (kg) (continuous and categories), BMI (kg/m²) (continuous and categories), systolic BP (mmHg), diastolic BP (mmHg), pulse rate (bpm), country and region.

In addition, the overall baseline NAS and 3 NAS sub-scores, the baseline fibrosis stage and the time since NASH diagnosis will be summarised.

Summaries of demographic data and baseline characteristics will be presented on the TS using both planned maintenance treatment and actual maintenance treatment.

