7.4.1 Primary analysis of the primary endpoint(s)

The primary analysis of the primary endpoint will be performed on the TS using actual maintenance treatment, and using all post-baseline biopsy data (as above). Patients without post-baseline biopsy (whether this is expected or not) will be imputed as non-responders in this analysis.

A logistic regression will first be performed on the primary endpoint to estimate the treatment effects of multiple doses of Survodutide and placebo, together with the corresponding variance-covariance matrix. Applying the Multiple Comparison Procedures and Modelling (MCPMod) approach, these estimates will then be further used to test for a non-flat dose response curve and to identify suitable dose-response shapes out of a selection of candidate models.

The MCPMod approach [R10-1424, R15-4293] is implemented in two main steps: (1) trial design stage; (2) trial analysis stage. The procedures for the trial design stage, including the selection of candidate models covering a suitable range of dose-response shapes, are provided in the CTP Section 7.2.2. Additional details for the trial analysis stage are specified below.

Logistic regression

The responses for each dose group, as well as their variance-covariance matrix, for the primary endpoint will be estimated using a logistic regression (using a logit link via PROC LOGISTIC in SAS®). The logistic regression model will be fitted without an intercept, and will include presence of diabetes of any type [yes, no], baseline fibrosis score [F1, F2, F3] and the dose group as factors. In the case that 0 events are observed in any combination of dose group and strata, a penalized regression based on the Firth bias reduction method [R20-2291] will be used. The subsequent MCPMod analysis will be fully carried out on the logit scale, and the graphical displays of the fitted models in the Mod step will then be converted from the logit scale to the probability scale for interpretation reasons.

A summary table will be produced of the logistic regression results, including estimated odds ratios for the comparison of each Survodutide dose against placebo and their 95% confidence intervals and associated p-values.

MCPMod

The “DoseFinding” package [R15-2001] will be used for MCPMod analysis.

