7.5.2 Secondary endpoint(s)

MCPMod dose finding analyses will only be performed for secondary endpoints where specified below. [REDACTED]

MRI-PDFF responder secondary endpoint - main analysis

Frequency tables will be produced of the MRI-PDFF responder secondary endpoint (percentage reduction of at least 30% from baseline in liver fat content, measured in units of % using MRI-PDFF, after 48 weeks of treatment) in both of the following ways:

- TS, actual maintenance treatment, using all post-baseline MRI-PDFF data within the Week 48 visit window (see [Section 6.7](#)), both on- and off-treatment (see [Section 6.1.6](#))
- TS, planned maintenance treatment, using all post-baseline MRI-PDFF data within the Week 48 visit window, both on- and off-treatment.

The above frequency tables will be displayed similarly to those for the primary endpoint.

The frequency tables will be produced overall, and further split by each of the subgroups defined in [Section 6.4](#).

Similarly to the primary endpoint analysis described in [Section 7.4.1](#), a logistic regression will first be performed on the MRI-PDFF responder secondary endpoint to estimate the treatment effects of the Survodutide doses and placebo, together with the corresponding variance-covariance matrix. The MCPMod approach will then use these estimates to test for a non-flat dose response curve and to identify suitable dose-response shapes out of a selection of candidate models.

The logistic regression model will be fitted without an intercept, and will include presence of diabetes of any type [yes, no], baseline fibrosis score [F1, F2, F3] and the dose group as factors, and baseline liver fat content (assessed by MRI-PDFF) as a continuous linear covariate. In the case that 0 events are observed in any combination of dose group and strata, the Firth bias reduction method will again be used. The subsequent MCPMod analysis will again be fully carried out on the logit scale, with conversion from the logit scale to the probability scale for interpretation.

A summary table will be produced of the logistic regression results, including estimated odds ratios for the comparison of each Survodutide dose against placebo and their 95% confidence intervals and associated p-values.

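### The visible primary logistic model omits baseline NAS, an already collected covariate that could give a small, optional gain in precision

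*SAP*

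**What the plan says.** Protocol 7.2.2 lists the terms of the primary model as "presence of diabetes of any type (yes, no) and baseline fibrosis stage (F1, F2, F3), as well as the dose group, as factors", and SAP 7.4.1 repeats them: the model "will include presence of diabetes of any type [yes, no], baseline fibrosis score [F1, F2, F3] and the dose group as factors". The log odds per dose and their covariance matrix then go into MCPMod.

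The NAS half of the endpoint is defined in SAP 5.1 as "Decrease of at least 2 points in NAS, with at least 1 point decrease in NAS sub-score of either lobular inflammation or ballooning". The other half is no worsening of fibrosis. SAP 7.1 already summarises "the overall baseline NAS and 3 NAS sub-scores".

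Elsewhere the plan adjusts for the baseline of the quantity being measured. The MRI-PDFF responder model, which also feeds MCPMod, adds "baseline liver fat content (assessed by MRI-PDFF) as a continuous linear covariate" (SAP 7.5.2, in line with Protocol 7.2.3). The protocol's repeated-measures model for continuous endpoints takes the baseline value as covariate: "baseline liver fat content or baseline NAS, as relevant".

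Randomisation is stratified by diabetes only (Protocol 7.4).

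**The concern.** The primary model adjusts for the baseline of the fibrosis component but not of the NAS component, and no reason is visible. The other MCPMod endpoint does adjust for its own baseline.

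If baseline NAS predicts response, the variation it explains stays in the error. The cost is some precision in the difference in proportions, which is the scale of the main objective, and some power of the contrast test. Chance imbalance in NAS between groups is part of that same variance, not a separate problem. The trial plans no confirmatory testing (Protocol 7.1), so the stakes are low.

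**Working it through.** **Inputs from the documents.** Four groups of 60; response 20% on placebo and 45% at the top dose; one-sided 5% family-wise error; six candidate shapes; target effect 20 points (Protocol 7.2.2 and 7.5, SAP 7.4.1). F1 is capped at 30% (Protocol 3.3).

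**Assumed, not in the documents.** Baseline NAS 4 to 8 with mean 5.4 and SD 1.1; diabetes 40%; F1/F2/F3 30/35/35%; odds ratio (OR) for response 1.0 to 2.0 per NAS point. Over the four points from NAS 4 to 8, ORs of 1.3, 1.6 and 2.0 mean 1.3^4 = 2.9, 1.6^4 = 6.6 and 2.0^4 = 16-fold odds, so the top of the range is generous.

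**Rates.** Linear on the logit scale: logit p(d) = -1.386 + 1.186 × d/6, giving 20.0, 28.7, 39.2 and 45.0%. Expected responders: 60 × (0.200 + 0.287 + 0.392 + 0.450) ≈ 80.

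**Method.** Each simulated data set is fitted with and without NAS.
- Standardised proportion for dose k: p_k = (1/N) Σ_i expit(α_k + x_i'β), averaged over all patients.
- MCPMod input: logit(p_k), with delta-method covariance S = D J V J' D, where V is the coefficient covariance, J the derivatives of p_k, and D = diag[1/(p_k(1 - p_k))].
- Optimal contrast for shape μ_m: c_m ∝ S⁻¹[μ_m - 1(1'S⁻¹μ_m)/(1'S⁻¹1)]. Statistic: T_m = c_m'logit(p)/√(c_m'S c_m). Reject if the largest T_m exceeds the multivariate normal critical value (1.96 to 1.99).
- Shapes are then refitted by generalised least squares. The significant family with the smallest generalised AIC is kept, and the smallest dose with a 20-point difference is read from it.

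**The plan's own figures first.** Protocol Table 7.5:1 gives 92.1% for the MCPMod test and 75.9% overall success. Without NAS the simulation gives 92.3% and 76.8%. For the four unequal allocations, power is within 0.5 point of the protocol's 88.1 to 91.1%.

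**Effect of adding NAS** (40,000 trials per scenario, 60 per group; Monte Carlo SE of paired power changes 0.04 to 0.17 points):

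| OR per NAS point | 1.0 | 1.15 | 1.3 | 1.6 | 2.0 |
|---|---|---|---|---|---|
| Variance, 6.0 mg minus placebo | +0.4% | +0.1% | -1.4% | -5.4% | -11.0% |
| Power of MCP test (points) | -0.1 | 0.0 | +0.4 | +1.3 | +2.4 |
| Target dose found (points) | 0.0 | 0.0 | +0.2 | +0.3 | +1.0 |

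Scale check: the unadjusted SE of the difference is √(0.20 × 0.80/60 + 0.45 × 0.55/60) = 0.0824. An 11% cut in variance gives 0.0824 × √0.89 = 0.0777.

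**Variations.**
- 20% imputed non-responders: power +0.0, +0.2, +0.8, +2.0 points at OR 1.0, 1.3, 1.6, 2.0.
- The protocol's four unequal group sizes (20,000 trials): -0.1 to +0.1 at OR 1.0, +0.4 to +0.5 at 1.3, +1.4 to +1.6 at 1.6, +2.5 to +3.4 at 2.0. Target dose found: -0.2 to +0.9 points over all ORs.
- Type I error with and without NAS: 4.8 to 4.9%.

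**Second simulation** (2,500 trials per scenario). Diabetes and fibrosis are modestly prognostic, and the comparator is the planned analysis fed with raw log odds. Variance ratios at OR 1.0, 1.25, 1.5, 2.0 are 1.005, 0.990, 0.965, 0.889. The equivalent sample size, 240 divided by the ratio, is about 239, 242, 249, 270. Power goes from 92.6 to 92.3%, 93.0 to 93.1%, 93.2 to 93.9% and 93.3 to 95.7%, with simulation error about 0.5 point. The mean difference stays near 25 points.

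**Why standardise.** If NAS is added and logits are converted at mean covariates, a true 25.0-point difference shows as 25.6, 26.4 or 27.6 at OR 1.3, 1.6 or 2.0. The target dose rests on that scale.

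**Firth rule.** Penalisation applies "In the case that 0 events are observed in any combination of dose group and strata". The chance of no responders in a cell with share q is (1 - p q)^60; for diabetic F1 patients on placebo it is (1 - 0.20 × 0.12)^60 = 0.23. Over all cells, Firth is triggered in about 1% of trials if strata means diabetes, 6% if fibrosis, and 80% if both are crossed. Under the crossed reading, adding NAS changes power by -0.1, +0.5, +1.2, +2.5 points at OR 1.0, 1.3, 1.6, 2.0. Type I error is 4.0 to 4.2%, and the true 25.0 points averages 24.4 to 24.6, with or without NAS.

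**The case against.** This is not an error. Protocol and SAP agree on the model, covariate choice in an exploratory trial is a judgement, and the stated power uses binomial draws without covariates, so nothing claimed depends on NAS. All of that stands.

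The prognostic strength is unknown. Entry criteria require NAS of at least 4 with a point each in inflammation and ballooning, so every patient has room to respond. That weakens the most obvious reason for a link. At OR 1.3 with imputed non-responders the power gain is 0.2 point. This stands too, and is why the change is optional.

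The main simulation treats diabetes and fibrosis as unrelated to response and standardises both fits, so its comparator is not exactly the planned one. The second simulation removes both features and finds gains of the same size. The linear truth remains a limit: Protocol 4.1.2 expects 2.4 mg to be comparable to placebo, and the gains were not computed for such a shape.

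Text is redacted or missing in Protocol 7.2.2 and SAP 7.4.2, and SAP 6.4, cited for subgroups, is not visible. A NAS-adjusted or NAS-subgroup analysis may already exist.

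The SAP was revised in January 2024 over baseline readings in China, which makes a further optional change to the primary model less attractive. That is a fair argument for the sensitivity-analysis route.

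**Conclusion.** The point holds as an optional improvement. The visible primary model leaves out a baseline score that is already collected and underlies half of the endpoint, while the plan makes the matching adjustment for liver fat.

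Omitting NAS causes no bias of its own. The actual-dose groups are not purely randomised, but that is a separate matter. The gain ranges from none at OR 1.0 to 11.0% lower variance and 2.4 points of power at OR 2.0 with equal groups. Effects on finding a target dose are about 1 point or less.

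These sizes rest on the assumed NAS distribution and odds ratios, a linear dose response, and, for the unequal groups, dose reduction unrelated to NAS with response following the actual dose.

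**What to change.** Before unblinding:
- Add baseline NAS total score, from the first screening reading, as a linear covariate in the primary logistic regression and in its planned-treatment sensitivity analysis.
- Average the predicted probability for each dose group over the Treated Set. Use the logits of these standardised proportions, with delta-method covariance, as MCPMod input.
- Keep the target-dose rule of SAP 7.4.1, reading the 20-point difference from the final AIC-selected curve.
- Keep the Firth rule, but state which strata trigger it (dose by diabetes, by fibrosis, or by both crossed). Standardise the Firth fit in the same way, noting that it pulls proportions slightly toward 0.5. Defining the strata is worthwhile whatever is decided on NAS.

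If unblinding has occurred, or the primary model is to stay as it is, report the NAS-adjusted model as a labelled sensitivity analysis. Leave the fibrosis-improvement model unchanged.

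**Cost.** One more parameter against about 80 expected responders, a standardisation step, and no new data. If NAS is not prognostic, the variance rises by about 0.4 to 0.5% and power falls by about 0.1 to 0.3 point, which is within simulation error at the upper end. The covariate would mix digital readings from China with physical readings elsewhere (SAP 5.1).
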